3.10 Governance Framework

This will be a service evaluation with the research aspect and ethical approval will be sought through Public Health England's Public Health Research Ethics framework.

The Principle Investigator and Co-principle investigators are responsible for drafting, and approval of this protocol. Review will be through the Education Evaluation Steering Group (DfE, DHSC and PHE)

and Testing Initiatives Evaluation Board (membership includes independent academics - see Appendix 5).

Overall responsibility for the study rests with the Secretary of State at the Department of Health and Social Care. The Principal Investigator has responsibility for the day-to-day delivery of the study, and for that he/she will be accountable to the Independent Trial Steering Group (TSG) (see Appendix 3 for Terms of Reference). The Study PI will be a member of this group. Test results data will be monitored by an Independent Data Monitoring Committee (IDMC) (see Section 5.2), which will report into the Trial Steering Group. Terms of Reference of the IDMC can be found in Appendix 4.

Lists of membership of study governance bodies can be found in Appendix 6.

Prior to enrollment of potential participant schools into the study advice will be sought from the local Director of Public Health, wider local authority and PHE on their willingness for the school to participate.

In the event of a suspect outbreak in a school (defined as more than 4 positive tests in a week), the local DPH and HPT will be responsible (with cooperation from the study team) for outbreak response management. Local and regional public health and teaching officials (including head teachers and school governing bodies) may raise concerns and questions with the Trial Steering Group for operational matters and the IDMC for other matters.

3.11 Testing Devices and Consumables

The following testing devices will be used in the study:

- Lateral Flow Antigen Testing Device for Daily Contact Testing: Orient Gene Coronavirus Ag Rapid Test
- qRT-PCR: Standard NHS T&T PCR throat and/or nasal swabs

3.12 Study Implementation Phasing

The study will be implemented in a phased manner to ensure the operational delivery model and intervention have received user feedback on feasibility and appropriateness prior to roll out across all sites. The aim is to maximise the effectiveness of the DCT implementation and minimise unnecessary burden of schools or participants

- Phase 1 Mixed methods feasibility trial in all students and staff in 6 schools
 - Confirm that the operational delivery model and data capture processes are viable and feasible for use at scale (or refine accordingly)
 - Gain user feedback (through PPI and focus groups/interviews) on all aspects of the trial and intervention procedures and materials (including guidance on how to interpret an LFD result), and refine procedures and materials accordingly
 - Gain user feedback on the tolerability of the proposed PCR testing regime, and refine accordingly
 - In this phase only the in-school assisted testing ATS delivery model will be available
- Phase 2 Deliver evaluation in full sample size of schools

- Collect evidence against objectives in full sample of schools
- At the start of this phase only the in-school assisted testing ATS delivery model will be available. If the at-home self-test delivery model becomes available during Phase 2 schools will be notified and allowed to choose to deliver the active case finding component via at-home self testing.
- Separately, collect evidence on home self-test DCT as this option becomes available

3.13 User Experience Research in Phase 1

In Phase 1, user feedback will be solicited on the public health intervention (including communication materials, consent forms and patient information sheets) and research elements of the evaluation. This will be used to refine the study operational model prior to scaling the number of sites in Phase 2.

4. Testing Regimen and Public Health Intervention

Participation in both the weekly active case finding and DCT components of the study will be (separately) voluntary. There are two options for first-order close contacts in the operation of this study, depending on whether they are taking part in the DCT component or not:

- Those taking part in the DCT component of the evaluation: people in the first-order close contact group of a positive index case are tested at the start of each day by anterior nares swab for LFD and on days 2 and 7 additionally with a throat-and-nose swab for qRT-PCR (anterior nares swabbing may be used if throat-and-nose swabbing is not tolerated)⁹.
- 2. Those not taking part in the DCT component of the evaluation: People in the first-order close contact group of a positive index case self-isolate in line with current national guidance. This option should be available for anyone who wishes to self-isolate rather than participate in the 'Daily Contact Testing' study. It will not be described further in this document.

Informed Consent from staff members and students and/or their parent /guardian will be required to take part in the testing components of the study. An information leaflet will be used to describe the purpose and process of the study, and the risks and benefits associated with the use of lateral flow antigen tests.

The below (which will be followed in all participating schools) focuses on the process for testing and the public health intervention. This is also illustrated in Figure 3 and Figure 4 below.

4.1 Initial Active Case Finding

This applies for students/ staff undergoing routine Lateral Flow Antigen Testing Device (LFD) tests through the national programme of school asymptomatic testing. For schools enrolled as part of Daily Contact Testing, at least weekly LFD testing is a prerequisite. LFD antigen testing will be via supervised anterior nares swabbing, and device use will be assisted use within a school's ATS model. The workforce for this will be trained according to national NHS T&T standard process.

Active case finding LFD testing will be once a week for students and twice a week for staff.

The following actions will be taken depending on the result:

4.1.1 Negative LFD Result

All persons who test **negative** on the weekly antigen LFD testing may participate in activities in the school with appropriate social distancing, respiratory hygiene, hand washing and face coverings where appropriate in line with the national guidance:

https://www.gov.uk/government/collections/guidance-for-schools-coronavirus-covid-19

⁹ For clarity, the day on which they are notified they are a contact is Day 0

4.1.2 Positive LFD Result

- The school should follow the national guidance (link above), in the same way as if the person with the positive test had become symptomatic whilst in school. The person in question must begin self-isolation in accordance with national guidance and Stay at Home guidelines¹⁰.
- Residential schools must follow the national guidance for residential educational settings: https://www.gov.uk/government/publications/coronavirus-COVID-19-guidance-on-isolation-for-residential-educational-settings/coronavirus-COVID-19-guidance-on-isolation-for-residential-educational-settings.
- Participants testing positive will be given a home PCR testing kit. They should be instructed to take a PCR swab **that day** and return it as per the enclosed instructions. This sample will be subject to genomic sequencing to allow chains of transmission to be analysed.

4.2 Management of First-Order Contacts of a Positive Index Case

Schools are eligible for the study on the condition that national guidelines and advice for good contact management are maintained throughout, with a pragmatic approach to the non-mixing of contact groups, and national guidance for schools continues to be followed.

This part of the protocol applies to asymptomatic first-order close contacts of COVID-19 positive index cases in the school who have tested positive through:

- Weekly asymptomatic LFD testing within the school
- Asymptomatic testing via another non-school route
- Symptomatic qRT-PCR testing outside the context of the school's testing programme

Any first-order close contact group where a positive index case is detected (by any means) will be eligible for Daily Contact Testing on the basis that:

- 1. The index case is a student / staff member at that school. First-order contacts of index cases not based in the school are not eligible for DCT within this evaluation
- 2. The first-order contact has consented to partake of DCT
- 3. The first-order contact is not a household contact of a currently COVID-19 positive individual (including the index case)
- 4. The first-order contact is not symptomatic

As stated above, participating schools must commit to maintaining the same level of good contact management and national guidance for schools. A pragmatic approach should be taken to ensure individuals participating in DCT should not mix with individuals from other contact groups (even if those individuals are also undergoing DCT).

Symptomatic individuals must follow national guidance (link above) and self isolate whilst awaiting results of a qRT-PCR test.

¹⁰ COVID-19: guidance for households with possible coronavirus infection - GOV.UK (www.gov.uk)

Note on timings of DCT / self-isolation compared to date of contact

Where the index case was identified via weekly asymptomatic LFD active case finding testing within the school, the date of their positive test will be treated as Day 0 for their first-order contacts' DCT / self-isolation regime (e.g., if an index case test's positive during weekly active case finding on Monday, Day 1 of their first-order close contacts' DCT regime would be Tuesday). When the index case was diagnosed outside of in-school testing, they will be asked during contact tracing when the last date of contact was with each of their named first-order contacts. This will allow the interval between the date of contact and the date of initiation of DCT / self-isolation (Day 1) to be calculated for the purpose of tracing chains of transmission.

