3.6 Assessment of End-Points

Please see the glossary at the start of this protocol for definitions

Co-Primary End-Points

(i) Number of school days missed among those eligible to be in school.

Daily school attendances will be obtained from the school register and absences recorded with reconciliation with COVID-19 associated absences. This will be compared between study arms, to historic schools' data, and to national schools' benchmark data collected via a survey of non-participating schools.

(ii) Estimated number of in-school COVID-19 transmission events

The number of positive cases will be obtained from the following sources:

- 1. Weekly LFD active case finding (Control and Intervention Arms)
- 2. Symptomatic individuals' NHS Test and Trace results obtained from Community Testing routine data (Control and Intervention Arms)
- 3. In-school LFD DCT testing (Interventional Arm).

Positivity rates will be reported for each source separately to facilitate like-for-like comparison between arms

Epidemiological links between cases will be obtained from the NHS Test & Trace Contact Tracing and Advice Service data base. Additional links will be obtained by membership of school-reported contact groups. Onward transmission from the index case will be determined by the following:

• Genomic sequence of virus: The additional PCR swab collected from positive individuals will be used to determine the whole genomic sequence of isolates. A sample of apparent links will be assessed with comparisons of whole genome sequencing. The diversity of genetic sequences both in the schools and the

community (routinely determined by COG) will be used to help interpret the results. Preliminary work currently undertaken will determine the appropriate genetic distance to be used to exclude a direct transmission event between individuals. This is likely to be 2 SNPs.

- Plausible epidemiological link (e.g. membership of same close contact group)
- For positive individuals identified in DCT the DMIC will review all available data to determine if the individual's infection was likely to have resulted from onward transmission from the index case, or via co-infection from an unknown 'upstream' positive or out-of-school positive case.

Secondary End-Points

(iii) Number of positive first-order contacts missed by daily LFD testing (Intervention arm only).

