The number of Covid-19-associated missed days at school is dependent on the number of positive cases identified and the number of contacts of these cases that are self-isolating. Each positive case is self-isolated for 10 days. In the control group all first order contacts will also be self-isolated for 10 days. It is expected that this trial will occur in the summer term when the number of cases in a school will be low. For instance, it is expected that in the control group about 30% of children (and their parents) will consent to participate in regular weekly active case finding testing. For the purposes of the power calculation, it is assumed that the expected number of index cases identified is about 1 outbreak/month. Each index cases will lead to identification of 50 children in their bubble who will need to self-isolate each for 10 days. The number of index cases identified is a Poisson distribution with mean 1/month with each index cases leading to 510 missed school days.

In the intervention group, it is expected that a more complex set of interactions will occur. The ability to avoid self-isolation by DCT is likely to make participation in weekly active case finding testing more

⁸ Quartagrio et al, 'Handling an uncertain control group event risk in non-inferiority trials: non-inferiority frontiers and the power-stabilising transformation' (2020)

attractive with an increase in consent to voluntary weekly active case finding testing to 60%. This in turn will lead to the identification of more positive cases with initially an expected number of 2 different index cases identified per week. However, it is expected that 70% of children will volunteer for DCT and therefore only 15 children (25% of 50) will self-isolate. In addition, about 2 contacts will be identified by LFD testing as positive during DCT (5% of 35). It is expected that these 2 children will only have contacts within the bubble and therefore they will not lead to identification of more children. In all, each index cases will lead to the index cases or 360 missed schools / month

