In addition, the intervention will lead, over time, to a decrease in transmission and therefore detection of cases through an increased identification and isolation of true positives, itself arising from an increase of uptake of weekly active case finding testing. However, this decrease will be offset by the possible increase in in-school transmission by infectious children not undertaking DCT who attend school.

It is expected that the trial will start in the Summer term with 100 schools enrolled into each arm. However, it is likely that only 50% of enrolled schools will manage to sustain the trial leaving only 50 schools in each group.

	Control Group	Intervention Group
Number of schools successfully participating	50	50
Proportion of children consenting to mass testing	30%	40-60%
Initial number of outbreaks detected/school	1/month	2/month
Number self-isolating (incl. index case and) each for 10 days	51	10-30
Number of schools in each arm	50	50

*Including index case and 2 cases in each DCT bubble of 50 children test positive and therefore need 10 days of self-isolation

Table 1: Assumptions in Power calculation

The number of schools required in each arm to determine whether school attendance has been increased by the intervention will depend on the number of children volunteering for DCT and the increase in the proportion of children consenting for weekly active case finding testing.

Assuming that 30% of the control arm participate in weekly active case finding testing, the number of schools per arm for a two month study is shown in the following table (power of 80%, two-sided alpha (0.05))

Number (per index case) in intervention group	Proportion if children consenting to weekly active case finding testing in intervention arm		
self-isolating and not undertaking DCT	40%	50%	60%
7	10	12	14
8	11	13	15

911141810121521111317241214192913152236141826451518305816203579172343112182653170192967172033871172138117				
11 13 17 24 12 14 19 29 13 15 22 36 14 18 26 45 15 18 30 58 16 20 35 79 17 23 43 112 18 26 53 170 19 29 67	9	11	14	18
12 14 19 29 13 15 22 36 14 18 26 45 15 18 30 58 16 20 35 79 17 23 43 112 18 26 53 170 19 29 67 17 20 33 87 112 21 38 117 117	10	12	15	21
13 15 22 36 14 18 26 45 15 18 30 58 16 20 35 79 17 23 43 112 18 26 53 170 19 29 67 1 20 33 87 1 21 38 117 17	11	13	17	24
14 18 26 45 15 18 30 58 16 20 35 79 17 23 43 112 18 26 53 170 19 29 67	12	14	19	29
15 18 30 58 16 20 35 79 17 23 43 112 18 26 53 170 19 29 67	13	15	22	36

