5.3 Results Data Monitoring

During the trial the combined results of all schools in the trial will remain blinded to all except the statistical centre and the Independent Data Monitoring Committee (IDMC). The IDMC will review the overall quality, safety and efficacy of the data and make recommendations to the Trial Steering Committee on whether the trial protocol should be altered. If they have evidence beyond reasonable doubt that one strategy is clearly superior (or inferior) to another arm and that the result is likely to change public health practice, they should immediately report the unblinded data and their recommendation to the Trial Steering Committee.

Statistical Analysis of primary and secondary end-points

Conventional statistical analysis will be undertaken. Analysis will be undertaken for the primary objective at a per-school basis with comparisons to the population of control schools. Absent school days (both total and COVID-related) will be presented as a proportion of pupils (with binomial confidence intervals). Unadjusted transmission events will be measured as the incidence of all COVID-19 positive cases determined by both Pillar 2 and school directed testing. Transmission events will also be categorised as 'more likely' if they either have a similar genetic sequence (the cut off to be determined) or as a member of the same predefined school bubble.

Secondary analysis

The performance of DCT will be made at the level of each primary contact. The performance of the DCT will be compared to PCR using conventional exact binomial statistics. The extent of secondary transmission events will be analysed using Poisson statistics and the results

stratified according to the LFD and PCR results of the DCT-contact. The results can also be adjusted according to the day that the LFD becomes positive and the CT value of the PCR result.

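### Attack rates (iv) and (v) pool index cases from all detection routes, although the plan expects weekly-testing uptake, and so possibly the mix of index cases, to differ by arm

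*Protocol*

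**What the plan says.** The protocol's definitions allow an index case to be found by asymptomatic LFD testing in or outside school, or by symptomatic PCR. Section 4.2 lists the same routes and makes contacts eligible whichever applies: "Any first-order close contact group where a positive index case is detected (by any means) will be eligible for Daily Contact Testing". That sentence governs eligibility for DCT. The pooling in the analysis comes from the definitions and from section 3.6 (iv) and (v), which take the contacts of all index cases.

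Section 3.9 expects the arms to differ in screening. For control: "in the control group about 30% of children (and their parents) will consent to participate in regular weekly active case finding testing". For the DCT arm, the chance to avoid isolation is expected to make testing more appealing, "with an increase in consent to voluntary weekly active case finding testing to 60" per cent. Table 1 gives a range of 40-60% in its row "Proportion of children consenting to mass testing". The stated consequence is: "This in turn will lead to the identification of more positive cases".

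For co-primary endpoint (ii), section 3.6 plans a split by source: "Positivity rates will be reported for each source separately to facilitate like-for-like comparison between arms". Nothing comparable is stated for (iv) or (v). Under secondary analysis, section 5.3 has secondary transmission results "stratified according to the LFD and PCR results of the DCT-contact", with possible further adjustment for the day of LFD positivity and the CT value.

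**The concern.** An attack rate per index case is conditional on the index case having been detected. If one arm screens more, it adds index cases found by screening, and the two arms' rates are then averages over different sets of index cases. If cases found by screening transmit less, or are caught earlier, the added clusters lower the average without any infection being prevented.

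The stratifier named in section 5.3 does not deal with this. It describes the contact's own test results, which arise after exposure, and not how the index case came to light. The protocol sees the need for a like-for-like comparison under (ii) but does not carry it to the attack rates. Section 3.7 says that positivity in second-order contacts will be used to judge the public health effectiveness of DCT, so a crude arm ratio could be read as an effect on transmission.

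**Working it through.** **1. Is higher detection in the DCT arm really the plan's premise?** Table 2 can be reproduced with

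n per arm = (1.960 + 0.842)² × (m1·51² + m2·(k+3)²) / (m1·51 − m2·(k+3))²

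Here m1 = 2 index cases per control school over two months, m2 = 2 × uptake/30%, and k is the number of contacts isolating; the index case and 2 LFD positives make k+3. For k = 15:

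- 40% uptake (m2 = 2.67): 7.849 × 6066/54² = 16.3, so 17 (printed 18)
- 50% uptake (m2 = 3.33): 7.849 × 6282/42² = 27.95, so 28 (printed 30)
- 60% uptake (m2 = 4): 7.849 × 6498/30² = 56.7, so 57 (printed 58)

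Over all 49 printed cells, 48 are matched to within 1 or 2 schools and one differs by 3. The sample size therefore scales index-case detection in proportion to weekly-testing uptake. (The text of section 3.9 says 2 index cases per week in the DCT arm, while Table 1 says 2 per month. These must be reconciled, but the steps below use only the uptake ratio.)

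**2. How far could the mix move?** Let a be the share of control index cases found by screening and f the uptake ratio (60/30 = 2, or 40/30 = 1.33). If only screened cases rise, the DCT-arm share is f·a/(f·a + 1 − a).

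- f = 2: a = 25%, 50%, 75% becomes 40%, 67%, 86%
- f = 1.33: a = 50% becomes 57%

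The protocol does not give a.

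**3. What does that do to the crude attack-rate ratio when DCT has no effect?** Attack rates by route are assumptions: 5-6% after symptomatic and 2-3% after screened index cases. With s = 1 − a symptomatic in control:

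- Control rate = s·S + (1−s)·A
- DCT rate = [s·S + f(1−s)·A] / [s + f(1−s)]

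| f | s | S v A | Control | DCT | Ratio |
|---|---|---|---|---|---|
| 2 | 50% | 6% v 2% | 4.00% | (3 + 2)/1.5 = 3.33% | 0.83 |
| 2 | 75% | 6% v 2% | 5.00% | (4.5 + 1)/1.25 = 4.40% | 0.88 |
| 2 | 25% | 5% v 3% | 3.50% | (1.25 + 4.5)/1.75 = 3.29% | 0.94 |
| 1.33 | 50% | 6% v 2% | 4.00% | (3 + 1.33)/1.167 = 3.71% | 0.93 |
| 1.33 | 75% | 5% v 3% | 4.50% | (3.75 + 1)/1.083 = 4.38% | 0.97 |

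Across s = 25-75% and these attack rates, the ratio is about 0.83-0.94 at 60% uptake and about 0.93-0.97 at 40%. If S = A it is 1.

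**4. Is there an opposing effect?** Section 3.6 (iv) counts infected first-order contacts by daily LFD, which only the DCT arm has, plus symptomatic PCR. Suppose a fraction q of infected contacts is found through symptoms in both arms, and DCT at the planned 70% uptake finds part of the rest, with LFD sensitivity Se assumed to be 0.4-0.8. The ratio is then [q + (1−q) × 0.7 × Se]/q.

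- q = 0.5: (0.5 + 0.5 × 0.28)/0.5 = 1.28, up to (0.5 + 0.5 × 0.56)/0.5 = 1.56
- q = 0.7: (0.7 + 0.3 × 0.28)/0.7 = 1.12, up to (0.7 + 0.3 × 0.56)/0.7 = 1.24

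On these assumptions the opposing effect on (iv) is often the larger of the two.

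**The case against.** A reader might infer that the comparison is biased in favour of DCT. The documents do not support that. They give neither the share of index cases by route nor infectiousness by route, and step 4 shows an opposing effect on (iv). For (v), school-based second-order contacts who take part are assessed by weekly LFD, and its expected difference in uptake could also raise the count in the DCT arm.

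A reader might also take the doubling of index cases in Table 1 to imply ratios as low as 0.75 or 0.70. With symptomatic cases held fixed, 0.75 needs screened cases to go from 0.5 to 1.5, a threefold rise: (3 + 3)/2 = 3.0% against 4.0%. The 0.70 needs 0.25 to become 1.25, a fivefold rise: (4.5 + 2.5)/2 = 3.5% against 5.0%. Doubled uptake does not produce either. Taken literally, the plan's proportional scaling (S + A = 1 and S + 2A = 2, with S and A here counts of symptomatic and screened cases) gives S = 0, so every index case comes from screening and the mix does not move. A shift needs a symptomatic or outside-testing share, which the protocol provides for but does not quantify.

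It is also fair to say that strata for secondary endpoints are commonly left to an analysis plan, that section 5.3 excludes nothing, and that higher uptake is part of the policy being compared. The last point stands against making a route-adjusted ratio the main result: route is itself affected by arm, and more screening may remove some would-be symptomatic index cases from that stratum in the DCT arm. It does not remove the concern. The benefit of uptake shows in school-level incidence, whereas a ratio per detected index case can change simply because different cases were detected. Moreover, the protocol is not merely silent: it defines the pooled denominator and names a stratifier that does not address the mix.

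**Conclusion.** The point holds in a limited form. Endpoints (iv) and (v) compare contacts of index cases selected after randomisation, under screening uptake that the plan itself expects to differ (about 30% against 40-60%), and no split by index detection route is stated.

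The case-mix effect alone would put the crude ratio at about 0.83-0.94 with uptake doubled, on the assumption that screened index cases transmit less (2-3% against 5-6%) and that 25-75% of control index cases are symptomatic. It is smaller at 40% uptake and absent at equal infectiousness. None of these route figures is in the protocol. No net direction can be claimed. The opposing effects cannot be assumed to cancel, so the crude ratio alone does not isolate what DCT does to transmission. These are secondary endpoints, and the matter is a cheap improvement to reporting.

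**What to change.** Keep the overall policy comparison of (iv) and (v). Beside it, report both rates by arm within index-case detection route: school weekly LFD, other asymptomatic testing, symptomatic PCR. Add a route-standardised ratio as a supporting analysis, not as the main estimate. State that the crude attack-rate ratio will not be read on its own as an effect of DCT on transmission.

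The cost is a few sentences of analysis text. Detection route should already be known, since section 4.2 handles contact timing differently for index cases found by in-school testing and for those diagnosed elsewhere. The downsides are wider intervals within routes, and strata that are themselves partly selected by arm. Reporting by route does not cure the difference in how infected contacts are found in the two arms, so that limitation should be stated alongside.
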